6.3.4 Smartphone-based ambulatory assessment

The ambulatory assessment will be conducted via the m-Path app installed on the participants' own smartphones. The app is available for Android and iOS smartphones. It will prompt participants to fill out a short questionnaire six times per day by sending a push-notification. And participants will be asked to take pictures of every food or drink (except of water) and upload these pictures through the m-Path app. Data from the assessments is saved encrypted on a secure GDPR-compliant server in the EU and will be matched to the other collected data using a pseudonymized alpha-numeric code.

Table 2. Measures applied in the ambulatory assessment phase.

All beeps		References
Affective well-being	MOOD-zoom + extra items??	
Vitality	Subjective Vitality Scales (state)	(Bertrams et al., 2020)
Alertness	Karolinska Sleepiness Scale	(Akerstedt & Gillberg, 1990)
Daily Experiences	Stressor Occurrence	
	Uplift Occurrence	
Current Situation	Place	
	Activity	
	Social contact	
	Light sources	
	Perception of current light	(M. G. Figueiro et al., 2021)
Morning only		
Sleep parameters	CONSENSUS sleep diary	(Carney et al., 2012)
Sleep quality	Adapted PROMIS sleep disturbance short form	
Evening only		
Cognitive Function	2-back task	As already implemented in m-Path
Health	Self-Rated Health	
	Physical Symptoms	(Larsen & Kasimatis, 1991)

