6.4 Measurement devices

All measurements within the framework of the research project are non-invasive, except for placing a continuous glucose monitor on the non-dominant forearm of participants from day 1 of the data collection period onwards.

Table 3 shows the different types and respective resolutions of the recorded data.

The continuous glucose monitor and the light sensor will be worn throughout the 12 days of the study, while the thermal skin sensors and the ambulatory blood pressure device will only be worn on day 11 and 12, between 08:30 and 17:00 h respectively.

Table 3. Data collected, methods and resolution.

Data	Unit	Device name	Frequency
Skin temperature	°C	iButtons	1 min
Interstitial glucose	mmol/L	Abbott Freestyle Pro IQ	15 min
Illuminance	Lux Melanopic EDI	Actlumus	1 min
Blood pressure	mmHg	ECGpro Holter-RR USB	15 min

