6.4.1 Actlumus wearable light sensor

Participants will wear a light logger around the neck like a pendant to log daily light exposure levels. The light logger is only worn during the day and taken off at night, or when participants get in contact with water (e.g. showering or swimming). We will be using the ActLumus by Condor Instruments, which is an actimeter with integrated light logger. The logger estimates melanopic EDI and photopic lux through several light channels. The logger is very lightweight (12-31 g) and can be clipped to the collar, cloth or worn around the neck or clipped onto glasses to measure light at eye-level. Data will be read locally using a cable and transferred to our computers (no cloud or external server involved) and analysed with a locally installed software from Condor Instruments called ActStudio.

Fig.2. Actlumus wearable light-logger

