6.5 Flowchart and Schedule

After a person expressed interest in participation, researchers will reply by sending the information letter and consent form via email. Subsequently, researchers will schedule a phone call during which they will provide a brief overview of the key aspects of the experiment and address any questions or concerns which participants may have. Additionally, this phone call will serve as an opportunity to evaluate participants' eligibility based on the inclusion and exclusion criteria (see 6.3.1. phone call screening).

Following the phone call and scheduling the participation days, participants will sign the informed consent form during the first visit at the University Hospital.

On day 1, each participant will undergo an eye examination and thereafter starts wearing the wearable sensors and receives instructions on how to complete the smartphone-based self-report forms are provided. After the ambulatory assessment period in participants' everyday life (days 2-10), participants will spend the 11th and 12th day in a controlled office room environment from 08:30 to 17:00 h. Between day 11 and 12, participants will leave controlled conditions from 17:00 h on day 11 to 08:30 h on day 12.

Throughout these 12 days, the sensors continuously record data until they are removed at the end of day 12. Flowchart 1 illustrates this 12-day study period.

[figure not shown]

Fig.6.: Flowchart of chronological events of participants enrolment in the study.

7 Risks

Overall, the study ensures that participants are exposed to conditions within the naturally occurring limits of daily life. We do not expect any risks from participating in the ambulatory assessment with previous research showing high acceptability and no noteworthy reactivity to measurement in participants' behavior. Nevertheless, on day 11 and 12 participants may be exposed to light conditions that could be perceived as uncomfortable compared to their preferences.

Blood pressure measurements will be performed on day 11 and 12 by means of an automatic inflatable cuff. These measurements might feel a bit uncomfortable, but do not induce negative health effects. After wearing the continuous glucose monitor for 12 days, skin irritation can occur from where the sensor wire is inserted.

The eye examinations bring no special risks for participants. Individuals might feel dazzled for a few seconds after the slitlamp examination, especially after retinoscopy.

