8.4 Primary and secondary study parameters

As the primary hypothesis of this study is that younger and older individuals differ in their light exposure patterns in everyday life, the primary outcome of this study is melanopic equivalent daylight illuminance (M-EDI) quantified in lux by the Actlumus wearable light sensor. M-EDI may differ between groups with respect to overall daily levels, exposure levels at different times of day (work-day vs. weekend-day), and the difference in exposure levels between work-days and weekend-days. Therefore, M-EDI will be statistically analysed between groups in the following three ways:

1. Compare the area under the curve (AUC) of M-EDI from day 1 to day 8 between young and old (unpaired t-test)

2. Averaging exposure levels over work-days and weekend-days in 1-hour time intervals over 24 hours and compare the two average 24-hour M-EDI patterns between young and old (2-way repeated measures ANOVA, factor 1 (between-subjects) group, factor 2 (within-subjects) time)
3. Averaging the onset of M-EDI in the morning hours and the offset in the evening over work-days and weekend-days and calculate the difference in onset and offset between the averaged work-day and weekend-day between groups (unpaired t-test)

The secondary hypotheses are that light exposure patterns in everyday life are linked to daily metabolic, cardiovascular and psychological outcomes, and that this link is stronger in individuals displaying less degeneration of eye structures.

Accordingly, mixed effects regression analyses will be performed to assess the relationship between different aspects of daily light exposure (momentary M-EDI, average daily exposure level, onset/offset; independent variables) and each of the daily health parameters (metabolic, cardiovascular, psychological functioning, and sleep; dependent variables). To evaluate the role of the degree of eye degeneration, an interaction term between light exposure and eye degeneration will be added to the regression models.

9 Ethics

The study must be approved by the Ethics Committee of RWTH Aachen University. The study is carried out in accordance with the Declaration of Helsinki (the latest version, established in Fortaleza, Brazil, 2013) and the Law on Medical Research involving Human Beings (WMO) and the General Data Protection Regulation (GDPR or GDPR).

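### In the secondary models, light onset and offset largely track rising and going to bed, so they will be associated with diary sleep timing and duration even if light has no effect.

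*Protocol*

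**What the plan says.** Protocol section 8.4 plans mixed models for the secondary hypotheses. The light predictors are "momentary M-EDI, average daily exposure level, onset/offset; independent variables" and the outcomes are "metabolic, cardiovascular, psychological functioning, and sleep; dependent variables". A light-by-eye-degeneration interaction is then added. The section gives no threshold or non-wear rule for onset and offset, and does not say which night's sleep is paired with which day's light.

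On wearing the logger, section 6.4.1 states: "The light logger is only worn during the day and taken off at night, or when participants get in contact with water". Section 6.4 states instead: "The continuous glucose monitor and the light sensor will be worn throughout the 12 days of the study". Section 6.5 adds that "the sensors continuously record data until they are removed at the end of day 12". These three statements do not agree.

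Table 2 in section 6.3.4 lists two morning sleep measures: sleep parameters from the "CONSENSUS sleep diary", whose items are not given, and a self-rated sleep disturbance form.

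**The concern.** A logger worn only by day gives its first reading of the day some time after rising and its last some time before bed. Unless onset and offset are defined otherwise, they largely mark those two moments. Diary bedtime, rise time and sleep duration are built from the same moments. A model of diary bedtime on light offset therefore comes close to regressing bedtime on itself. A model of sleep duration on offset regresses a difference that contains bedtime on a proxy for bedtime. Morning onset also comes after the waking that it would be predicting if it is paired with that morning's diary.

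At stake is one part of the secondary analysis. A significant onset/offset coefficient for sleep timing or duration could be reported as a link between everyday light and health, although the same coefficient would arise if light did nothing.

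**Working it through.** **Inputs from the protocol.** Two groups of 30, so 60 people (section 5). Nine everyday-life days, days 2 to 10 (section 6.5). Two-sided 0.05 (section 8.3). Participants are asked to hold their home bedtimes steady (section 3), which argues for including a small within-person bedtime spread. The protocol gives no figure for this analysis, so there is none to reproduce; the effect size in section 6.2 concerns the age comparison.

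**Assumptions, because the protocol gives no spreads.** Within-person SD of bedtime, S: 30, 45 or 60 min. SD of the gap between light offset and bedtime, G: 10 to 120 min. The small values represent offset read from logger removal; the large ones represent a definition that places offset far from bedtime. The gap is independent of bedtime. Light has no effect on any sleep outcome.

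**Formulas.**
- Offset = bedtime − gap, so the within-person correlation of offset with bedtime is r = S / √(S² + G²).
- Duration = rise time − bedtime. If rise time is independent of bedtime with the same SD, the correlation of offset with duration is −r / √2.
- If bedtime and rise time correlate at ρ with equal SDs, the slope of duration on offset is −(1 − ρ) × S² / (S² + G²).

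**Example.** S = 45, G = 30: r = 45 / √(2025 + 900) = 45 / 54.1 = 0.83, and the correlation with duration is −0.83 / 1.414 = −0.59.

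**Results: correlation of offset with bedtime / with duration.**

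| Bedtime SD (min) | gap SD 10 | 20 | 30 | 60 | 120 |
|---|---|---|---|---|---|
| 30 | 0.95 / −0.67 | 0.83 / −0.59 | 0.71 / −0.50 | 0.45 / −0.32 | 0.24 / −0.17 |
| 45 | 0.98 / −0.69 | 0.91 / −0.65 | 0.83 / −0.59 | 0.60 / −0.42 | 0.35 / −0.25 |
| 60 | 0.99 / −0.70 | 0.95 / −0.67 | 0.89 / −0.63 | 0.71 / −0.50 | 0.45 / −0.32 |

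A simulation (60 people, 9 days, 300 runs per cell, person-mean centred) agreed with these values to within 0.01. The within-person slope was significant in every run for bedtime and in 97 to 100% of runs for duration. For a sleep-quality score generated independently of timing, the correlation was about 0 and 3 to 9% of runs were significant, around the nominal 5%.

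**Sensitivity to the bedtime–rise correlation.** With ρ = 0.3 and S = 45 min, the slope of duration on offset is −0.7 × 2025 / 2250 = −0.63 h per hour for G = 15 min, and −0.7 × 2025 / 2925 = −0.48 h per hour for G = 30 min. Each hour of later offset would thus appear to cost 38 or 29 minutes of sleep (0.63 × 60 and 0.48 × 60). In the weakest setting tried with ρ = 0.3 (S = 30 min, G = 120 min), 90% of runs were still significant.

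**Does the conflict over wear time matter?** If the logger did record through the night, as sections 6.4 and 6.5 suggest, evening light would still end around bedtime when the lights go out. The overlap remains whichever statement is right.

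**Does the pairing of days matter?** Matching a day's light to the next morning's diary separates morning onset from the rise time that precedes it. It does not separate evening offset from the bedtime that follows. Pairing alone is therefore not a sufficient repair.

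**The case against.** The strongest reply is that onset and offset are not yet defined. An analysis plan that is not shown may use an illuminance threshold that puts them hours away from rising and bedtime. This stands in part: the correlation then falls towards 0.24 to 0.45 (gap SD 120 min). It does not vanish, and with 60 people over nine days it is still nearly always significant. The pairing of onset/offset with sleep is stated in the protocol itself, so it is not a detail left open.

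It is also fair that putting the logger on after rising is inferred from daytime wear, that the diary's items are not listed, that every SD is assumed, and that section 8.4 speaks of relationships rather than causes.

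Four stronger readings are tempting and are not supported:

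- *That the whole light–sleep analysis is compromised.* The sleep disturbance form is not a clock time, and nothing ties it to logger wear by construction. Momentary and average light are also outside the argument.
- *That the secondary hypothesis as a whole would rest on an artefact.* Its wording names metabolic, cardiovascular and psychological outcomes; sleep appears only in the list of model outcomes. The non-sleep models are not touched.
- *That a false interaction with eye degeneration would follow.* An overlap common to everyone gives no reason for a steeper slope with less degeneration. It would need wear habits or bedtime regularity to differ with degeneration, and the protocol gives no evidence of that.
- *That primary analysis 3 is circular.* It compares work-day and weekend differences in onset and offset between age groups and has no sleep outcome.

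**Conclusion.** The concern holds for one predictor (light onset/offset) against one part of the sleep domain (diary timing and duration). There, an association is built in with no light effect. The offset–bedtime correlation is about 0.7 to 0.99 when the gap SD is 10 to 30 min and about 0.24 to 0.7 when it is 1 to 2 h, for within-person bedtime SDs of 0.5 to 1 h. Onset behaves the same way towards rise time if it is paired with that morning's diary. A significance test of these coefficients would carry almost no information about light.

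This rests on three assumptions: the spreads above, a diary that yields bedtime, rise time or duration, and an onset and offset that follow rising and going to bed. The figures show direction and range and are not an estimate for this study. Because the analysis is secondary and the repair is cheap, the change is one that should be made, but it does not threaten the primary comparison.

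**What to change.** In section 8.4, for diary sleep timing and duration:

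1. Do not count onset/offset coefficients as evidence of a light–health link. Drop them or label them descriptive.
2. Use light-level predictors computed within verified wear time, such as mean log melanopic illuminance in a fixed window before diary bedtime, and the daytime mean.
3. State that light on day d is paired with the diary completed on the morning of day d+1.

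Reconcile sections 6.4, 6.4.1 and 6.5 on when the logger is worn, because verified wear time depends on it.

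The cost is a few sentences in section 8.4 and some additional processing of the light data. The measurements needed are already planned. The downside is that the association of onset/offset with sleep timing and duration is no longer reported as support for the secondary hypothesis.

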
1. Background

Within a day, the Earth rotates once around its own axis, causing predictable changes in light conditions throughout the day. In this context, humans have developed the ability to synchronize their physiological processes to a period length of around 24 hours, adapting to these recurring fluctuations. Our ambient light hence has a major influence on our physiology and psychology depending on the time of day. However, over the last century our relationship to light has drastically changed: our current “indoor society” spends about 90% of awake time indoors exposed to lower light intensities (e.g. up to 300 lux for typical electric office lighting) than outside in natural daylight (e.g. up to 100,000 lux on a sunny day), along with excessive exposure to artificial light during the evening beyond sunset. Yet, studies on the impact of daytime light exposure patterns are limited (Fleury et al., 2020). A chronic lack of daylight in combination with excessive light in the evening is increasingly being considered as a risk factor in the aging society's rising incidence of cardiovascular, metabolic, and psychological disorders. For example, experiencing darker days and brighter nights was associated with a higher risk for the onset of several psychological disorders such as depression or psychosis (Burns et al., 2023). In terms of short-term effects on potential mediating mechanisms, Harmsen et al. previously showed that bright light during office hours induced mostly favorable acute effects on glucose control and thermoregulation in older insulin-resistant volunteers compared to dim light (Harmsen et al., 2022) and that natural office lighting through windows improved glucose control in older type 2 diabetes patients (Harmsen et al., 2022). Similarly, when workers were exposed to higher levels of light during their workday, they reported increased vitality and lower depressive symptoms (Mariana G. Figueiro et al., 2017; Nagare et al., 2021). However, to date, there is only limited data on how light exposure patterns differ across the lifespan (Scheuermaier et al., 2010) and how aging may affect the influence of light on our physiology and psychology. First findings indicate that younger and older adults show different emotional effects of exposure to blue light (Sletten et al., 2009), but these differences have so far not been addressed in daily life.

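### The momentary light–health models in Protocol 8.4 list no time-of-day term, so a daily rhythm shared by light and the outcome can be credited to light

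*Protocol*

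**What the plan says.** Protocol 8.4 outlines the secondary models in two sentences. The predictors are "momentary M-EDI, average daily exposure level, onset/offset; independent variables". The outcomes are "each of the daily health parameters (metabolic, cardiovascular, psychological functioning, and sleep; dependent variables"). For the role of the eye, "an interaction term between light exposure and eye degeneration will be added to the regression models". No other fixed effect, random-effects structure or centring of light is named, and nothing says that the list is complete.

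Two other places bear on this. The Background (section 1) says that humans "synchronize their physiological processes to a period length of around 24 hours" and that ambient light has a "major influence on our physiology and psychology depending on the time of day". In 8.4 itself, clock time is an explicit factor in the second primary analysis, where light is the outcome: "2-way repeated measures ANOVA, factor 1 (between-subjects) group, factor 2 (within-subjects) time". Section 6.3.4 supplies the momentary self-reports: the app asks participants to "fill out a short questionnaire six times per day". Section 6.4 supplies glucose every 15 minutes.

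**The concern.** On the protocol's own premise, clock time drives both the exposure and the outcomes. Light is high around midday and low in the evening, and mood, vitality, sleepiness and glucose may also vary over the day. A regression of a momentary outcome on momentary M-EDI without clock time gives light the credit for whatever the outcome does at those hours. The same slope then enters the interaction with eye degeneration.

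The light–health link is part of the first main goal in section 2, and the interaction serves the second. Time is modelled where light is the outcome, but is not named where light is the predictor, which is where leaving it out biases the estimate.

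**Working it through.** The protocol states no figure for these models. Its n = 30 per group and d of about 0.7 (section 6.2) concern the age-group comparison, so there is nothing to reproduce here.

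**Inputs from the protocol.** 60 participants (section 5), six prompts a day (6.3.4), nine free-living days, days 2–10 (6.5), two-sided 5% level (8.3). That makes 60 × 9 × 6 = 3,240 prompts if all are answered.

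**Assumed inputs.** log10 M-EDI follows a cosine peaking at 14:00 with amplitude 0.9 and within-person residual SD 0.6. The outcome has residual SD 1 and a cosine rhythm of peak amplitude A. There is no light effect. The protocol does not give the prompt times; two schedules, 2.5 h apart within the day, are used.

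**In-phase rhythm.** Let v be the variance over the prompt times of the cosine with its peak at 14:00.
- Variance of light = 0.81v + 0.36
- Spurious slope = 0.9·A·v / (0.81v + 0.36)
- SE ≈ 1 / √(3,240 × variance of light)

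*Prompts 09:00 to 21:30.* The cosine values are 0.259, 0.793, 1, 0.793, 0.259 and −0.383, with mean 0.454 and mean square 0.423, so v = 0.423 − 0.206 = 0.217. Variance of light = 0.176 + 0.36 = 0.536. Slope = 0.365A. SE = 0.024.

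*Prompts 08:00 to 20:30.* v = 0.1755. Variance of light = 0.142 + 0.36 = 0.502. Slope = 0.315A. SE = 0.0248.

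| A | z (09:00–21:30) | false positives, formula | z (08:00–20:30) | false positives, formula | false positives, simulated |
|---|---|---|---|---|---|
| 0.1 | 1.52 | 33% | 1.27 | 25% | 20–42% |
| 0.2 | 3.04 | 86% | 2.54 | 72% | 72–94% |
| 0.4 | 6.08 | 100% | 5.08 | 100% | about 100% |

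The simulated column pools null simulations, some of which also include a between-person light–outcome correlation of 0.5. An antiphase rhythm gives the same rates with the sign of the slope reversed.

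**With hour of day in the model.** Simulated false positives were 4.5–8% in the main set (200 data sets per setting, Monte Carlo SE about 1.5 points) and 4–6% in others. With no outcome rhythm, the light-only model also holds its level (5.5%).

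**Phase.** If the outcome peaks later than light by an angle δ, v in the numerator becomes v·cos δ + k·sin δ, where k is the covariance of the cosine and sine over the prompt times.
- Prompts 08:00–20:30, k = −0.028. Peak 4 h later: 0.088 − 0.024 = 0.064, or 36% of the in-phase slope; simulated rates 6–48% over A = 0.1 to 0.4. Shift of 6 h: 16% of the slope; simulated 5–11%. Peak 4 h earlier: 0.088 + 0.024 = 0.112, or 64%.
- Prompts 09:00–21:30, k = −0.129. Peak 4 h later: 0.109 − 0.112, close to zero. Peak 4 h earlier: 0.109 + 0.112 = 0.220, no reduction. Shift of 6 h: 0.129/0.217 = 59% of the slope.

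A phase difference can therefore remove most of the bias, but how much depends on its direction and on the prompt times.

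**Cost in precision.** Hour terms leave 0.36 of the light variance. The SE factor is √(0.536/0.36) = 1.22 here, and √(0.59/0.36) = 1.28 with a larger assumed daily light swing.

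**Centring alone.** Person-mean centring without hour terms left simulated false positives at 29–32%, 82–91% and 100% for A = 0.1, 0.2 and 0.4. Leaving light uncentred added only about 0.01 to the slope when the between-person correlation was 0.5.

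**The case against.** The strongest reply is that 8.4 is an outline. It names no random effects or error structure, so it cannot be the full model, and covariates and centring are commonly left to a statistical analysis plan. A reader might infer from the text that clock time is deliberately excluded; the document does not say so, and the second primary analysis shows that the authors do think about it. What remains is that 8.4 does fix the predictors and one added term, and that this set is confounded on the Background's own premise.

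Second, the hypothesis speaks of a link, not a causal effect, and the causal contrast comes from the randomised bright and dim days over the same hours (sections 3 and 8.3). That comparison is indeed untouched. But a link produced only by the clock says little about sensitivity to light, which is what the interaction is meant to test.

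Third, a reader might infer that the secondary hypothesis would be confirmed with near certainty even if light did nothing. The documents do not support that. The high rates need an outcome rhythm of sufficient size, suitably aligned with light, and full prompt compliance; the documents give neither amplitude nor phase for any outcome.

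Fourth, a reader might blame the missing within-person and between-person split for the rhythm problem. It is a different issue, and centring does not cure the confounding.

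**Conclusion.** The point holds for models that pair momentary M-EDI with momentary glucose or momentary self-reports. Fitted as listed, they can show a light effect that is only a shared daily rhythm, often so for quite small rhythms in phase or antiphase with light. The sizes rest on the assumed cosine rhythms, variances, prompt times and full compliance. They describe the six-a-day self-reports; the 15-minute glucose series was not simulated, though the mechanism is the same.

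The scope is limited. Daily-average and onset/offset predictors, and sleep, are not exposed to this mechanism. Blood pressure barely is, since it is recorded only on days 11 and 12 under one set light level per day. The primary hypothesis and the paired bright–dim comparison are unaffected. The within/between mixing is a separate matter of lesser weight: it blurs what the slope and its interaction with eye degeneration mean.

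**What to change.** State in 8.4 that every model with momentary M-EDI as a predictor includes hour of day, either categorical or as harmonic terms. The data needed are already being collected. The cost is a sentence of specification and an SE of the light slope about 20–30% larger in the simulated set-ups, because less light variance remains after time of day is removed.

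Separately, and with lower priority, enter light as a person-mean-centred term plus the person mean, and say which of the two interacts with eye degeneration. This keeps the two levels apart but does not replace the hour term.

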Growing evidence suggest that the effects of light on health parameters vary dramatically across individuals, yet recommendations for appropriate light exposure in real-life settings rarely take these individual differences into account (Chellappa, 2021). In this context, age has been identified as a moderator of light sensitivity (Chellappa, 2021), but the underlying mechanisms remain elusive. Therefore, this interdisciplinary project will for the first time explore the contribution of aging processes within the eye to an individual's sensitivity to light and its health effects. The degeneration of the lens associated with cataract is a natural aging process that affects the amount of light that can reach the retina. Cataract affects around 17% in the general population worldwide and up to 54% in the over-60 age group (Hashemi et al., 2020). Replacing the lenses of the eye by surgery largely restores light transmission and has been shown to improve the sleep-wake rhythm, the release of the sleep hormone melatonin, light sensitivity, and sleep quality (Brøndsted et al., 2017; Giménez et al., 2016). Depending on how far the degeneration of the lens and retina have progressed and/or whether surgical intervention has taken place, large individual differences in sensitivity to different ambient light can therefore be expected. However, this aging process is ignored by most previous attempts to study the physiological and psychological health effects of light.

2. Aim of the study

With the primary hypothesis of this study being that younger and older individuals differ in their light exposure patterns in everyday life, the two main goals of the AgeLight study are to:

- characterize light exposure patterns in younger and older adults and their link to cardiovascular, metabolic, and psychological health
- identify determining factors of an individual's sensitivity to light and its health effects (such as degeneration of the lens and retina)

3. Study design

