In summary, there are no side effects, exposures, or complications associated with this study.

Medical benefits. The study has no direct medical benefit to the participants. However, the results form the basis for suggesting improvements in light exposure behaviour for health purposes and thus provide a basis for aspects of disease prevention and health promotion. In addition, if something abnormal is noted with respect to the eye examination, daily blood

sugar levels and blood pressure, participants will be informed and advised to seek a medical health professional.

Unexpected medical findings. With wearing the continuous glucose monitor and the blood pressure cuff as well as eye examinations, there is a small risk of unexpected medical findings. These unexpected findings could be revealed based on abnormal blood sugar levels (i.e. indicative of type 1 or 2 diabetes mellitus, and hypoglycemia, respectively), or abnormal blood pressure levels (i.e. indicative of cardiovascular issues), or eye degeneration (i.e. for which surgery could be recommended). In case of such unexpected findings, a physician (Institute of Ophthalmology) will inform the individual participant and discuss further steps. Prior to such a conversation, the right of the participant not to know is taken into account.

Dealing with COVID-19-related risks. According to WHO, there is no pandemic situation (*Statement on the Fifteenth Meeting of the IHR (2005) Emergency Committee on the COVID-19 Pandemic*, n.d.).

8 Statistical analysis

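### Section 8.4 does not require light to precede the outcome: for mood, vitality and sleepiness the whole-day average and evening offset include light after the rating, and for sleep the pairing is left open

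*Protocol*

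**What the plan says.** Section 8.4 plans mixed effects regressions with "different aspects of daily light exposure (momentary M-EDI, average daily exposure level, onset/offset; independent variables" as predictors. The same sentence sets the whole-day predictors against the outcomes, with psychological functioning and sleep named among them: "average daily exposure level, onset/offset; independent variables) and each of the daily health parameters (metabolic, cardiovascular, psychological functioning, and sleep; dependent variables". An interaction with eye degeneration is to be added. No lag, exposure window or merge rule is given. The hypothesis is worded as an association: "light exposure patterns in everyday life are linked to daily metabolic, cardiovascular and psychological outcomes".

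Section 6.3.4 fixes when the outcomes are taken. The app asks participants to "fill out a short questionnaire six times per day by sending a push-notification". Table 2 puts affective well-being, vitality and alertness in every prompt. Sleep ("CONSENSUS sleep diary" and a sleep disturbance short form) is in the morning prompt only. The 2-back task, self-rated health and physical symptoms are in the evening prompt only.

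Two other places read the link as an effect of light. Section 2 aims to "identify determining factors of an individual's sensitivity to light and its health effects", and section 7, under medical benefits, says that "the results form the basis for suggesting improvements in light exposure behaviour for health purposes".

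**The concern.** A low mood or a bad night can keep a person indoors afterwards. If the light variable contains light from after the rating, that behaviour enters the coefficient, and a regression with light as the independent variable presents it as light being related to mood or sleep.

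Under a purely descriptive reading this is tolerable. It is not tolerable if the results are to support advice on light behaviour, which needs light to come first. It also matters for the interaction. A stronger link in people with less eye degeneration is a natural prediction if light acts through the eye, but not if mood drives time spent outdoors. Section 6.2 expects degeneration to differ substantially between the age groups, so an age difference in staying indoors after a bad night or low mood could look like the hypothesised interaction.

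**Working it through.** The protocol gives no figure on this point, so there is none to reproduce.

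**Inputs from the protocol.** 60 people (section 5); days 2 to 10 as full free-living days, hence 9 per person (section 6.5); six prompts a day and a morning sleep report (6.3.4, Table 2); light logged every minute over 12 days, with the logger off at night (6.4, Table 3, 6.4.1); two-sided 5% level (8.3).

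**Assumptions, not in the protocol.** Even spacing of prompts; a reverse effect g of 0 to 0.3 SD; no true effect of light; outcomes independent between days and prompts once person level is removed.

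**Step 1: order of events.**
- Prompt-level outcomes against momentary M-EDI: light is taken at the rating, with no later light included.
- Prompt-level outcomes against same-day average or evening offset: later light is included for nearly every prompt. Averaging mood over the day does not help, because outcome and exposure then overlap.
- Morning sleep report against the preceding day's light: correct order.
- Morning sleep report against the light of the same calendar day: reversed order.
- Evening-only outcomes against the day's average: most of the light comes first.

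**Step 2: share of the waking day after a prompt.** With prompts at fractions k/5 of the day, k = 0 to 5, the remaining shares are 1, 0.8, 0.6, 0.4, 0.2 and 0. The mean is 3.0/6 = 0.5. Prompts at the midpoints of six equal intervals also average 0.5. This is a share of time; it is a share of light only if light is spread evenly.

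**Step 3: what the models return when light does nothing.** 2,000 simulated studies of 60 people x 9 days, within-person slope, cluster-robust standard error. For sleep, light on a day is g times the preceding night's within-person deviation plus noise. For mood, each rating shifts light in the next interval by g, and the day has seven intervals.

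| g (SD) | Sleep, light after the night | Sleep, light before the night | Mood, whole-day mean | Mood, light before the prompt |
|---|---|---|---|---|
| 0 | 5% | 5% | 5% | 5% |
| 0.1 | 61% | 7% | 55% | 4% |
| 0.2 | 99% | 8% | 98% | 6% |
| 0.3 | 100% | 12% | 100% | 6% |

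Entries are the percentages of studies significant at two-sided 5%.

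**Step 4: checks by formula.**
- Sleep, light after the night: expected slope g/(1 + g²) = 0.099, 0.192, 0.275; simulated 0.100, 0.193, 0.276.
- Mood, whole-day mean of seven intervals: expected slope 7g/(7 + 6g²) = 0.099, 0.193, 0.279; simulated 0.100, 0.192, 0.278.
- Rejection rate for sleep at a within-person correlation of 0.10: 540 - 60 - 1 = 479 df, t = 0.10 x √479 / √(1 - 0.01) = 2.20, power about 0.60, close to the simulated 61%.
- Sleep, light before the night: the excess over 5% fits the small bias from centring on a nine-day mean, about -g/9 = -0.011, -0.022, -0.033; simulated -0.013, -0.023, -0.033.

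**The case against.** The strongest objection concerns sleep. A reader might infer that 8.4 regresses each night on the light of the day that follows it, so that the path from a day's light to the next night goes untested. The text does not say this. Matching a day's light to the next morning's report is equally compatible with it, and evening offset as a predictor of sleep most naturally points to the following night. Lags and merge rules are also commonly left to an analysis plan, which is not at hand here. That part of the objection stands: for sleep, the protocol is silent rather than wrong.

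Second, momentary M-EDI is in the list and is the natural predictor for prompt-level ratings. This stands in part. It is listed alongside the whole-day variables, not in place of them, and 8.4 applies the list to each outcome.

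Third, the hypothesis speaks of a link. If poor sleep lowers later light, a link exists, and detecting it is not a false positive for that wording. So the rejection rates above are not type I error rates for the hypothesis as written; they show how often a reverse path would be read as an effect of light. The aims and the intended advice invite that reading.

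Fourth, the randomised bright/dim comparison on days 11 and 12 tests light effects experimentally. It does, but for office hours on two days. It does not settle the free-living associations or their interaction with eye degeneration as planned in 8.4, and the night after day 12 is not recorded.

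**Conclusion.** The point holds for mood, vitality and sleepiness: 8.4 names predictors that contain light from after the rating, on average about half of the waking day under evenly spaced prompts. Under assumed reverse effects of 0.1 to 0.3 SD and no light effect, the whole-day mean gives a significant mood coefficient in 55 to 100% of studies, against 4 to 6% with light before the prompt.

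For sleep it is a matter of clarification. The result depends on a pairing that the protocol does not choose: 61 to 100% with light after the night, 7 to 12% with light before it.

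The protocol gives no effect sizes for the reverse path, so these rates show sensitivity and do not predict what this study will find. Evening-only outcomes are little affected, and the primary outcome is untouched. The change is worth making before analysis because it costs almost nothing and decides what these secondary models can support.

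**What to change.** State the time order in 8.4:
- Pair each morning sleep report with the light of the preceding day, including its offset.
- For outcomes rated at every prompt, make momentary M-EDI, or mean M-EDI from waking (or over a fixed window) up to the prompt, the main predictor.
- Keep the whole-day mean for evening-only outcomes. If it is also reported for prompt-level outcomes, label it as association only and show the reverse lag as a check.

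The one-minute light data already support this, so the cost is a few sentences and a merge rule. One sleep record per person has no full preceding day of light, because collection starts at about 18:00 on day 1. Time order does not remove all reverse influence: if mood or sleep carries over from one report to the next, earlier light may still reflect an earlier outcome, and the simulation above assumes no such carry-over.
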